~33	6-Month Follow-Up Assessment	Clinical interview, immediate treatment interview, & self-report battery (7 measures), treatment satisfaction

Note. Behavior therapy involves the introduction, teaching, in-session and between-session practice, and mastery of behavioral therapeutic techniques designed to improve symptoms of depression and anxiety, including behavioral activation (BAT group) as well as situational, physical, thought, and emotional exposures (transdiagnostic CBT group). Final treatment session will take place between sessions 12-16, as determined by provider and participants' collective decision. Final treatment session will involve relapse prevention content. Post-treatment assessment will be completed 1 week immediately after final treatment session. 6-month follow-up assessment will be completed 6-months after final treatment session.

Randomization Procedures

Participants will be randomly assigned (1:1) to one of the two study arms (*n* = 48 per arm) using a permuted block randomization procedure. Randomization will be stratified by principal diagnostic group and block size will be varied to minimize the likelihood of unmasking. After determining eligibility and completing consent and baseline assessment materials, enrolled participants will be assigned to treatment groups by the Project Research Assistant using a computer generated randomization scheme. Once a participant is randomized and attends the first session, they will be included in the intent-to-treat analysis. Randomization will occur at the participant level. As such, we will take the following steps to minimize contamination between the two arms of the study: 1) only one member of a household will be eligible for enrollment; and 2) other VAMC providers will be informed of their patients' participation in the study, but will be blinded to the treatment condition of their patients.

Transdiagnostic CBT Treatment Condition

As noted above in the Preliminary Studies section, a transdiagnostic CBT protocol was developed and revised through two demonstration studies and one focus group. The resulting protocol involves several primary components, including psychoeducation on the symptoms of depression and anxiety (session 1), assessment of motivation and setup of treatment plans (session 2), exposure therapy (sessions 3-15), and relapse prevention (final session). In addition to these primary components, optional modules are included to supplement exposure

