All therapy will be delivered by a Project Masters-Level Therapist, trained and supervised by the Principal Investigator ([name]). Training of treatment staff will involve mastery of the two treatment protocols, completion of two practice participants for each protocol, and review of all practice sessions by Principal Investigator in order to assess/minimize therapist drift between the two protocols. Consistent with other well-designed treatment outcome studies, all treatment sessions will be audio recorded with 20% of sessions randomly selected for review for treatment integrity and fidelity. These integrity and fidelity reviews will focus on evaluating the match between the treatment manuals and the material covered in session (e.g., treatment components introduced/reviewed, in session exercise, and homework assigned). To evaluate adherence, rating forms will be developed by the Principal Investigator and based upon the treatment manuals to determine if the therapist appropriately covered the content of each session (i.e., demonstrated the particular behavior described in each item). These rating forms use 7-point Likert scale response formats, and are modeled after the therapist rating forms used in other studies of CBTs. Staff will be recruited and trained and then asked to rate the recordings independently to allow for the computation of inter-rater reliability. If participants request changes to their mental health medications at any time during the treatment, a medication consult will be completed with their existing providers within the RHJ VAMC (e.g., [name] for patients recruited from Primary Care Mental Health Integration program) with changes in medications recorded for inclusion in the analyses as a possible covariate.

Assessment of Mental Health Symptoms, Quality of Life, and Treatment Satisfaction

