In preliminary hypothesis testing, efficacy outcome variables will be compared using the generalized linear mixed models (GLMM) approach. This approach provides a general framework that accommodates a wide range of data types (continuous, ordinal, dichotomous, categorical, count) and distributional assumptions (e.g. Gaussian, Binomial, Poisson) and accommodates repeated measures, covariate structure among repeated observations, and missing data. In the first set of primary hypothesis testing analyses, immediate post-treatment scores for each outcome of interest will be used (separately) as the dependent variable in the model, intervention (transdiagnostic CBT versus BAT control) will be included as the primary independent variable, and pre-treatment scores for the outcome of interest will be added as covariates. When approximate normality is assumed, GLMM reduces to a general linear models (GLM) approach which, in the simplest case (intervention as the primary independent variable with baseline level of outcome variable as covariate), is equivalent to a comparison of change from baseline scores for transdiagnostic CBT versus BAT control using an independent sample t-test. Additional covariates (e.g. age, number of psychiatric comorbidities, race, sex, combat theatre, and number of treatment sessions) will be added to the model to adjust for putative confounding variables. If intervention differences in other baseline variables are found in initial descriptive analyses, these variables will be also be added to the multivariable model. In secondary analyses, the modeling procedure will be repeated for the period between immediate post-treatment and 6-month follow-up. Given that we are seeking preliminary evidence of treatment

efficacy (to justify the next step in this line of research), there will be no adjustment for multiple outcomes or time points to avoid an overly conservative approach at this preliminary stage.

Feasibility and Acceptability Analyses (Primary Aim 2)

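### The plan leaves open adjusting the Aim 1 comparison for medication changes made after randomisation, which could take the arm coefficient away from the randomised effect

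*Combined protocol and SAP*

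**What the plan says.** The text on medication is in section D, Treatment Training and Fidelity: "If participants request changes to their mental health medications at any time during the treatment, a medication consult will be completed with their existing providers", and the changes are noted "with changes in medications recorded for inclusion in the analyses as a possible covariate".

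On timing, Randomization Procedures states: "After determining eligibility and completing consent and baseline assessment materials, enrolled participants will be assigned to treatment groups". Therapy starts after that, so any change requested during therapy comes after randomisation.

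The model is in the Efficacy Measures Analyses for Primary Aim 1. The post-treatment score is the dependent variable, arm is the main independent variable, and "pre-treatment scores for the outcome of interest will be added as covariates". The text continues: "Additional covariates (e.g. age, number of psychiatric comorbidities, race, sex, combat theatre, and number of treatment sessions) will be added to the model". The stated purpose is "to adjust for putative confounding variables". Medication change is not named there, but the list is introduced by e.g. and so is not closed. The next sentence adds further variables only where the arms differ on them at baseline.

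No passage says when the medication term would be entered, whether a model containing it is primary or supportive, or how medication changes bear on the effect being estimated.

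**The concern.** A confounder of a randomised comparison has to precede allocation. A medication change requested in the course of therapy does not, so adjusting for it cannot serve the purpose that the plan gives for its covariates. It can do harm in two ways. If arm influences the changes and the changes influence the outcome, the term removes part of the effect of arm. If poor prognosis both prompts a request and worsens the outcome, the term compares the arms within groups that were selected after randomisation.

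The documents do not say why participants would ask for a change. They do give reasons why the arms might differ. Hypothesis 1 predicts greater symptom reduction with CBT, which would mean fewer requests in that arm if symptoms prompt them. Exposures belong to the CBT arm, and the Potential Risks section describes emotional discomfort as a familiar reaction to exposure-based treatment, which could push the other way.

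At stake is the meaning of the Aim 1 arm coefficient, in a plan that uses the between-arm difference to judge whether the treatment merits further study.

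**Working it through.** The documents give no figure on this point, so there is none to reproduce. From the documents: allocation is 1:1 with 48 per arm (2 × 48 = 96), at least 72 completers are targeted, and the core model is post score on arm plus baseline score. Everything else below is an assumption. Negative coefficients favour CBT.

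**What governs the shift.** With baseline balanced by randomisation, least squares gives

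adjusted arm coefficient = unadjusted arm coefficient − γ × (p_CBT − p_BAT),

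where γ is the coefficient of medication change in the adjusted model and p is the proportion changing medication in each arm. If arm does not affect the changes, the bracket is zero and nothing moves.

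**No true arm effect.** Assumptions: the medication is inert; an unmeasured prognosis variable worsens the outcome by 0.6 SD per SD and multiplies the odds of a change by OR per SD; the baseline effect is 0.5 SD; the outcome SD is 1. Large-sample results (2,000,000 per scenario):

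| Changes, BAT v CBT | OR | γ | Unadjusted | Adjusted |
|---|---|---|---|---|
| 20% v 30% | 2 | 0.38 | 0.00 | -0.04 |
| 20% v 30% | 4 | 0.63 | 0.00 | -0.06 |
| 20% v 40% | 2 | 0.38 | 0.00 | -0.08 |
| 20% v 40% | 4 | 0.63 | 0.00 | -0.12 |
| 30% v 20% | 2 | 0.38 | 0.00 | +0.04 |
| 30% v 20% | 4 | 0.63 | 0.00 | +0.06 |
| 25% v 25% | 4 | 0.64 | 0.00 | 0.00 |

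Check on the fourth row: 0 − 0.63 × (0.40 − 0.20) = -0.126, against -0.124 simulated.

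**True effect of 0.5 SD, requests driven by symptoms.** Assumptions: arm lowers mid-treatment symptoms by 0, 0.25 or 0.50 SD; the log-odds of a change rise by 0 to 1.5 per SD of those symptoms; a medication change improves the outcome by 0, 0.3 or 0.5 SD (1,000,000 per scenario). The unadjusted column is the randomised total effect, including any effect that runs through medication.

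| Mid-treatment effect | Log-odds per SD | Medication benefit | Changes, CBT v BAT | Unadjusted | Adjusted | Shift |
|---|---|---|---|---|---|---|
| 0 | 1.5 | 0 | 27% v 27% | -0.501 | -0.501 | 0% |
| 0.50 SD | 1.5 | 0 | 17% v 27% | -0.500 | -0.450 | -10% |
| 0.50 SD | 1.5 | 0.3 SD | 17% v 27% | -0.470 | -0.448 | -5% |
| 0.50 SD | 0.5 | 0.5 SD | 17% v 21% | -0.481 | -0.491 | +2% |

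Shift = (adjusted − unadjusted) / unadjusted; in the second row, (-0.450 + 0.500) / (-0.500) = -10%. A further set of assumptions (change rates 20-40%, OR 2-4, medication benefit 0-0.6 SD) gave -7% to +3%. The overall range is therefore about -10% to +3%.

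**Scale.** The standard error of a standardised difference is about √(2/48) = 0.20 SD with 48 per arm, or √(2/36) = 0.24 SD with 36. The largest null shift is 0.12 / 0.20 = 0.6 of a standard error. With complete data at N = 96 and a nominal 5% test, four of the unequal-rate null scenarios (20% v 30%, OR 2; 20% v 40%, OR 2 and 4; 30% v 20%, OR 4) gave false-positive rates of about 5% unadjusted and about 5% to 11% adjusted.

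**The case against.** A reader might infer that the plan will adjust for medication changes, that these changes are a response to how therapy is going, and that the Aim 1 estimate will therefore be biased. The documents support none of these as stated. The covariate is only a possible one, and the analysis section does not list it. The reason for a request is not given, and side effects or unrelated reasons fit the text equally well. Other providers are blinded to arm, which limits arm-driven prescribing, although it does not stop a participant's progress from prompting a request. A shift also needs arm to affect the changes; symptom-driven requests alone produce none.

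The plan also describes the difference in mean change from baseline, with a 95% CI and no mention of covariates, and uses it to judge clinical importance. The randomised contrast would probably be reported whatever else is fitted. Since changes are recorded, any imbalance between arms would be visible. The simulated shifts are modest and rest on assumptions, and the plan calls its efficacy evidence preliminary. Finally, number of sessions is a firmer case of adjustment for a post-randomisation variable: the Procedures section commits to it and the Aim 1 list names it.

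All of this stands, and it narrows the point. It does not remove it. No rule says which estimate takes precedence, the open list admits the medication term, and nothing marks a model containing it as supportive. Correcting the use of session count would leave the medication sentence as it is.

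**Conclusion.** The point holds in a limited form. The plan permits, without requiring, adjustment of the Aim 1 comparison for medication changes that arise after randomisation. Such a term cannot correct confounding. If arm affects the changes, it can move the arm coefficient away from the randomised effect.

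The size depends wholly on assumed change rates, prognosis links and medication effects: nil without an arm effect on changes, at most about 0.12 SD in the null scenarios tried, and about -10% to +3% of a true 0.5 SD effect. The sign cannot be fixed in advance, because the plausible mechanisms pull in opposite directions. The stronger reading, that the primary estimate is biased as planned, is not supported. Sample size is not affected. The change is still worth making, because the better rule is clear and nearly free.

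**What to change.** 1. In Treatment Training and Fidelity, end the sentence by saying that medication changes are recorded, *reported by arm and not entered in the Aim 1 model*, in place of their use as a possible covariate.
2. In the Efficacy Measures Analyses for Primary Aim 1, state that, as far as medication is concerned, only variables fixed before randomisation may enter the model. Without this, the open list would still admit the term.
3. Show any model adjusted for in-trial medication changes only as a labelled supportive analysis, beside the estimate from arm plus baseline score.

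The cost is one or two sentences and one descriptive table of changes by arm, from data already to be recorded. Adjusting for psychiatric medication status at baseline should not be offered as a free substitute. Eligibility screens for recent starts, but the demographic form has no medication item and the documents show no other form that collects it. None of this alters how medication requests are handled clinically.

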RCT of Transdiagnostic CBT

Objective

To evaluate the transdiagnostic CBT in a RCT of VAMC patients with depressive/anxiety disorders by investigating its preliminary efficacy in reducing symptomatology, comorbidity, and improving quality of life compared to BAT (psychotherapy control condition) at immediate post-treatment and 6-month follow-up. Patient satisfaction and predictors of feasibility (attendance and dropout) also will be assessed.

Recruitment Strategy

VAMC patients will be recruited through the Primary Care – Mental Health Integration program and CBT Clinic at the RHJ VAMC. Within these programs, all VAMC patients reporting symptoms of depression and anxiety meet with a mental health staff member to complete a diagnostic interview and self-report measures as part of their standard clinical practices. If VAMC patients endorse symptoms consistent with a depressive/anxiety disorder, the patient's interest in participating in research will be assessed and, if agreeable to research, patients will be put in contact with research staff (same day meeting and/or follow-up phone to schedule research assessment). A research assessment will be completed with the project staff to first complete consent documentation and then assess inclusion/exclusion criteria (with a targeted sample of 96 VAMC patients; \geq 72 completers), including a semi-structured clinical interview and self-report questionnaires focused on the psychiatric symptoms and quality of life (described later). Participants who meet diagnostic criteria for the targeted disorders will be randomized into a study condition, and will be assigned to a project therapist. Because most VAMC patients who meet study criteria likely will present with multiple depressive/anxiety disorders, principal diagnosis, or the most impairing of

the diagnosable disorders, will be used to select patients for participation. To balance diagnoses across the two conditions, a stratified random assignment based on principal diagnosis will be used for the most common principal diagnoses (MDD, PTSD, and PD). Based on new patient consults at the RJH VAMC (i.e., nearly 1000 in 2011 with at least one-half presenting with symptoms of an depressive/anxiety disorder), it is expected that \geq 50% of the recruited VAMC patients will have served in OEF/OIF and \geq 33% will be representative of minority groups.

Eligibility Criteria

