Our software (logical) security policy has three main components: 1) VAMC standard antiviral protection; 2) password policies; and 3) additional level of firewall protection. The National DVA maintains firewall protection. The backup schedule at the RHJ VAMC consists of fully-verified daily backups. The backup tapes, which are in current rotation, are stored locally.

All data will be entered into an SPSS database. The SPSS database will be created by the Principal Investigator and research assistant will be responsible for all data entry. Data quality and consistency checks (e.g., data range checks) will be integrated as part of the data entry procedure. Data quality will be monitored and assured in several ways: 1) as reported; and 2) as entered into the study database. For the former, all hardcopy data forms will be visually inspected by project staff prior to data entry. Furthermore, a manual comparison of randomly selected data hardcopy forms with data output generated from the SPSS database will be performed, and consistency checks will be generated as part of routine data cleaning procedures. All hardcopies of the data files will be stored in a locked file cabinet behind a locked door in the PI's office at the RHJ VAMC (B530). Hardcopies of the data will be destroyed/shredded at five years after the completion of the study.

Analysis Plan – Treatment Outcome Symptomatology and Feasibility

Preliminary Descriptive Analyses

Univariate descriptive statistics and frequency distributions will be calculated as appropriate for all relevant variables to identify potential departures from distributional assumptions of proposed analyses. If necessary, appropriate data transformations will be applied, or alternative analysis procedures (e.g., nonparametric) will be used. Baseline values for demographic and symptom variables will be described via frequency distributions for categorical variables, measures of central tendency (mean, median), and variability for the total sample and within race groups. The baseline variables will be compared between intervention groups using t-tests (or Wilcoxon rank sum tests) for continuous outcomes and chi-square (or Fisher's Exact Test) for categorical variables.

Missing Data

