The full intent to treat (ITT) analysis set will comprise all randomized participants. Missing data in the full analysis set will occur if participants drop out prior to the end of the study. Participants will not be discontinued from the study because of non-adherence and all will remain in the study unless consent is withdrawn or if there are concerns regarding participant safety. Missing data for the ITT analysis set will be imputed using multiple imputation methods. The results of analyses using study completers and protocol adherers (completer and perprotocol analyses) will be compared with results using the ITT analysis set to test sensitivity of study conclusions to study drop-outs and protocol non-adherence. In addition, the information on dropout proportion will be used as one of the outcome measures of intervention feasibility.

Efficacy (Symptomatology & Quality of Life) Measures Analyses (Primary Aim 1)

The continuous measures of intervention efficacy and quality of life are APPQ, DASS, IIRS, MASA, PCL, STICSA, and V/SF-36. The primary outcome time point is at the end of the active intervention phase (immediate post-treatment) and the secondary time point is at the end of the naturalistic 6-month follow-up period. The difference in mean change from baseline to end-of-active intervention (effect sizes) for transdiagnostic CBT versus BAT control condition will be estimated via 95% CI. For the secondary time-point analyses, transdiagnostic CBT versus BAT control differences in change from immediate end-of-intervention to the 6-month follow-up will also be estimated using 95% CI. By assessing the magnitude of the between-intervention-group differences, as described by the CI, clinicians can judge whether the novel intervention provides sufficient improvement in these outcomes to suggest a clinically significant result that warrants further investigation.

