Exploratory analyses using GLMM modeling, as described above, will be carried out to determine if there is a preliminary suggestion that the effect of the intervention on efficacy and acceptability outcomes differ by principal diagnosis. For these analyses, a diagnosis by intervention group interaction term will be included in the model. Trends toward significance for the diagnosis by intervention interaction term would provide suggestive evidence of a possible differential diagnosis effect, suggesting that the change in the outcome variable is different for disorder groups (e.g., depressive disorders versus anxiety disorders) or between specific disorders (e.g., PTSD versus MDD). It is acknowledged that this study may not be powered to fully evaluate the statistical significance of the diagnostic comparisons; however, for this preliminary study, trends toward statistical significance are sought for future hypothesis-driven study in a larger adequately powered trial, rather than confirmation of a hypothesized differential diagnosis effect. Similar exploratory analyses will be completed for race and combat theatre.

E. PROTECTION OF HUMAN SUBJECTS

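### The distribution check looks at variables rather than model residuals, and its open-ended fallback does not require the pre-treatment score to be kept

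*Combined protocol and SAP*

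**What the plan says.** Section D, Preliminary Descriptive Analyses, sets out the check: "Univariate descriptive statistics and frequency distributions will be calculated as appropriate for all relevant variables to identify potential departures from distributional assumptions of proposed analyses". The remedy follows: "If necessary, appropriate data transformations will be applied, or alternative analysis procedures (e.g., nonparametric) will be used". No test, threshold, order of preference or efficacy procedure is named, and nothing says whether covariates stay in the fallback. The Wilcoxon rank-sum test appears in that subsection only for comparing baseline variables between arms.

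The Primary Aim 1 subsection (efficacy measures) models each post-treatment score separately on arm, with the pre-treatment score as covariate, within a GLMM framework that can also take non-Gaussian outcomes. It also reports the between-arm difference in mean change with a 95% CI, and rests the clinical reading on it: "By assessing the magnitude of the between-intervention-group differences, as described by the CI, clinicians can judge" whether the improvement is sufficient.

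**The concern.** A linear model with a baseline covariate needs well-behaved residuals given arm and baseline. It does not need normally distributed scores. A marginal distribution can look far from normal while the residuals are acceptable, and the two come apart most on bounded symptom scales after effective treatment, when many scores sit near the minimum.

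The choice of analysis would be made once the outcome data are in, separately for seven instruments, and the plan applies no multiplicity adjustment. Two things are then at stake. First, a valid baseline-adjusted comparison could be replaced, without need, by a less powerful one. Second, a transformed or rank-based main analysis would not itself give an interval in scale points, which is what the clinical judgement uses.

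**Working it through.** **Inputs from the documents**
- Sample: recruitment is planned "with a targeted sample of 96 VAMC patients", with at least "72 completers" (Section D, Recruitment Strategy). "Participants will be randomly assigned (1:1) to one of the two study arms" (Randomization Procedures). The two totals agree at 25% dropout: 72 / (1 - 0.25) = 96. Completers per arm: 72 / 2 = 36.
- No effect size or target power is stated for the efficacy comparison, so there is no power figure to reproduce. Power is mentioned only for the exploratory analyses: "this study may not be powered to fully evaluate the statistical significance of the diagnostic comparisons".
- Two-sided 5% is assumed, in line with the wording "BAT control condition will be estimated via 95% CI".
- Pilot means, SDs, t values and n come from the second pilot table (Section C, Demonstration of Revised Transdiagnostic Protocol).

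**Step 1. Distance of post-treatment scores from the floor**, (post mean - minimum) / post SD. Minima follow from the item scoring: PCL 17 × 1, IIRS 13 × 1, DASS 0.

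| Scale | Calculation | SDs above minimum |
|---|---|---|
| DASS-Depression | 4.8 / 4.3 | 1.12 |
| PCL | (33.7 - 17) / 14.2 | 1.18 |
| IIRS | (37.3 - 13) / 17.6 | 1.38 |
| DASS-Anxiety | 5.0 / 3.5 | 1.43 |
| DASS-Stress | 7.0 / 3.9 | 1.79 |

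Means this close to the minimum imply truncated, skewed post-treatment distributions.

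**Step 2. Pre-post correlation implied by the pilot.** SDdiff = (pre - post) × √n / t, and r = (SDpre² + SDpost² - SDdiff²) / (2 × SDpre × SDpost).
- PCL: SDdiff = 22.8 × √22 / 7.2 = 14.85; r = (316.8 + 201.6 - 220.6) / 505.5 = 0.59.
- In the same way: IIRS 0.36, DASS-Depression 0.56, DASS-Anxiety 0.54, DASS-Stress 0.32.

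**Step 3. How often the check would fire.** Simulated trials used 36 per arm, the pilot-2 means, SDs and correlations, and scores clipped at the scale limits, with Shapiro-Wilk at 5% standing in for the unstated trigger. With both arms at the pilot post-treatment mean:
- Post scores of PCL, DASS-Depression, DASS-Anxiety and IIRS were flagged in about 52-98% of trials; DASS-Stress, furthest from its floor, in about 22%.
- Residuals of the baseline-adjusted model on the four scales were flagged in about 9-18%.
- Type I error of the linear model was 4-5%.

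The rate depends on where post-treatment scores lie. It is lower if an arm finishes well above the pilot mean and higher if it finishes below. A cruder check, clipping standardised post scores 1.15 SD below their mean, flagged almost every sample, and residuals in 25-55%.

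**Step 4. Cost if the fallback were an unadjusted rank-sum test.** At an assumed effect of 0.6 post-treatment SD:

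| Analysis | Power |
|---|---|
| Baseline-adjusted linear model | about 76-85% |
| Rank-sum, post scores | 65-71% |
| Rank-sum, change scores | 44-69% |
| Rank or log model keeping baseline | about 0-10 points below the linear model |

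**Step 5. Analytic cross-check for post scores.** Relative to the adjusted model, the rank-sum noncentrality is multiplied by √(0.955 × (1 - r²)). If the adjusted model has 80% power, its noncentrality is 1.96 + 0.84 = 2.80. For the PCL, √(0.955 × (1 - 0.59²)) = 0.79; 2.80 × 0.79 = 2.21; power = Φ(2.21 - 1.96) = 60%. Across the five pilot-2 correlations the result is 60-74%.

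**The case against.** The strongest reply is that the plan's wording is conditional and open. The switch happens only where necessary, no automatic test is specified, and a statistician who knows that the assumption concerns residuals need not switch because a marginal histogram is skewed. A transformation, a non-Gaussian GLMM or a rank ANCOVA would each keep the pre-treatment score. The testing is also described as preliminary. All of this is fair, and it limits the point to what the text leaves open.

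Four stronger readings are tempting, and the documents do not support them.
- *The plan discards the baseline score.* It does not say so. The rank-sum test is named only for baseline comparisons, and the efficacy model includes the pre-treatment score.
- *Mixed diagnoses trigger the switch almost by design.* In a separate two-group mixture simulation (36 per arm, no floor), pre or post scores were flagged in 7-12% of trials when diagnosis explained 0-40% of score variance, 30% at 55%, 45% at 60% and 85% only at 70%. A very wide PCL gap also conflicts with the pilot. Suppose 65.2% had PTSD (39.1 + 26.1) and the rest averaged an assumed 26. The PTSD mean would have to be (56.5 - 0.348 × 26) / 0.652 = about 73, and the between-group variance 0.652 × 0.348 × 46.8² = about 497, above the pilot's total variance of 17.8² = 317. The scale floor is the likelier trigger.
- *Power is halved.* For post scores this needs r of about 0.74-0.82 (for reference power of 50-90%), whereas the larger pilot gives 0.32-0.59. Only a rank-sum test on change scores comes near half, and only on some scales. On the PCL, change scores tripped the normality check in just 3-7% of trials.
- *The scale-point CI disappears.* The efficacy subsection commits to it separately, and the fallback sentence does not cancel it.

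One further concession stands. With strongly skewed scores a rank model that keeps baseline can be somewhat more powerful than the linear model.

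**Conclusion.** The point holds in a limited form. The check is aimed at the wrong quantity, and the fallback is unspecified and does not require the pre-treatment score to be kept. On the pilot-2 figures the univariate check would often raise an alarm (about 52-98% of trials on four scales) where residuals mostly would not (about 9-18%) and where the linear model is already valid. The cost depends on which fallback is chosen: about 0-10 points of power if baseline is kept, and a fall from about 76-85% to 65-71% or 44-69% if an unadjusted rank-sum test is used on post or change scores.

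These figures assume 36 per arm, normal scores clipped at the scale limits, a Shapiro-Wilk trigger, a 0.6 SD effect, and correlations back-calculated from rounded completer data on 22-23 patients. The documents give no pilot data for APPQ, MASA, STICSA or V/SF-36, so no figure is claimed for those. The point is worth correcting before analysis, but it does not undermine the trial.

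**What to change.** Replace the fallback sentence so that it states three things:
- Distributional checks are made on residuals of the baseline-adjusted model, not on univariate distributions.
- The raw-scale baseline-adjusted difference, with a heteroscedasticity-robust or bootstrap 95% CI, is the main efficacy result whatever the check shows, so the clinical judgement stays in scale points.
- Any rank-based or transformed analysis retains the pre-treatment score and is labelled a sensitivity analysis.

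This is a short edit to the analysis plan and needs no new data. The downside is small: outlier-prone or strongly skewed scales, where a rank model may be somewhat more powerful, are dealt with in the sensitivity analysis rather than the main one.
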